2. TRIAL OBJECTIVES AND ENDPOINTS

2.1 MAIN OBJECTIVES, PRIMARY AND SECONDARY ENDPOINTS

2.1.1 Main objectives

The primary objective of this phase III pivotal trial in CIAS is to assess the efficacy in improving cognitive impairment using MCCB in patients with schizophrenia treated for 26 weeks with Iclepertin 10mg as compared with placebo.

The key secondary objective is to assess the efficacy in daily functioning of 26-week treatment with Iclepertin 10mg as compared with placebo in terms of Schizophrenia Cognition Rating Scale (SCoRS) and Virtual Reality Functional Capacity Assessment Tool (VRFCAT).

The secondary objectives are to assess the efficacy in improving reasoning and problem solving and patients' experience of cognitive impairment associated with their disease.

Patients will be required to be on stable antipsychotic treatment at the time of inclusion.

The primary treatment effect of interest is defined in the primary estimand framework as specified in detail in Section 7. All efforts will be taken to continue to collect efficacy data at planned visits after patients discontinued trial treatment following an intercurrent event. For patients who discontinued trial treatment after intercurrent events that will be handled by the treatment policy approach, these observed off-treatment data will be included in the primary analysis. For patients who discontinued trial treatment after other intercurrent events that will not be handled by the treatment policy approach, these observed off-treatment data will be censored and excluded from the primary analysis.

In summary, the primary treatment effect of interest is the effect obtained at the primary time point if patients had stayed on the treatment, i.e. taking the trial medication for the full treatment duration while allowing the following intercurrent events: change in concomitant medications or background non-pharmacological therapy, change in study partner, and treatment interruption or discontinuation due to exacerbation, an acute episode, adverse events (AEs) that are considered drug related and protocol-defined drug withdrawal.

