¹ List of relevant medications will be provided as part of the ISF

- Strong or moderate CYP3A4 inducers including St. John's wort (Hypericum perforatum)
- Dietary supplements and herbal remedies that may impact cognition, in the investigator's judgement
- Antiepileptics (when used for the treatment of epilepsy)¹
- Tricyclic antidepressants
- Traditional Chinese medicine/ non-Western therapy
- Medical devices therapy (e.g. TMS, neurofeedback)
- 12. Patients who plan to change their current life-style habits including but not limited to alcohol, nicotine or caffeine use, or diet, during the treatment period.
- 13. Patients who have participated in a clinical trial with repeated assessments (i.e. a single assessment is not exclusionary) with the MCCB and/ or any other schizophrenia cognitive battery within 12 weeks prior to screening.
- 14. Any formal Cognitive Remediation Therapy (CRT) within 12 weeks prior to screening. Initiation of CRT is not allowed during the study.
- 15. Initiation or change in any type or frequency of psychotherapy (e.g. cognitive behavioral therapy, social skills training, vocational/occupational therapy) within 12 weeks prior to randomization. Patients with ongoing, stable psychotherapy for more than 12 weeks prior to randomization (and intend to maintain the same frequency during the study) may qualify as per clinical judgement of the investigator.
- 16. Any of the following, in the judgment of the investigator:
 - Clinically significant finding of the physical examination, vital signs (including blood pressure (BP) and pulse rate (PR)), ECG or laboratory value (as measured by the central laboratory) that would jeopardize the patient's safety while participating in the trial or their capability to participate in the trial.
 - Symptomatic/unstable/uncontrolled or clinically relevant concomitant disease or any other clinical condition that would jeopardize the patient's safety while participating in the trial or capability to participate in the trial.
 - Significant or unstable physical condition that may require change in medication or hospitalization that would impact cognitive function.
 - Planned major surgery requiring withdrawal from study medication for more than 2 weeks during the study period.
 - Note: Please contact sponsor in case of you have any questions.
- 17. Hb below lower limit of normal at Visit 1 assessed by the central lab.

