3.3.4.2 Permanent discontinuation of trial treatment

For all patients, the reason for permanent discontinuation from trial treatment (e.g. AEs) must be recorded in the eCRF. Patients who permanently discontinue from the trial after randomization will not be replaced.

Even if the trial treatment is permanently discontinued, the patient should remain in the trial and, given the patient's agreement:

- The patient will complete the early end of treatment (eEOT) and safety follow up visits.
- Additionally the patient will be followed according to the flow chart until the planned Visit11 (26 weeks).

Please refer to Flow Chart and section 6.2.3.4 and 6.2.4 for more information on continued trial participation.

An individual patient is to be withdrawn from trial treatment if:

- The patient wants to stop taking the trial treatment permanently.
- The patient exhibits suicidality, in the clinical judgement of the investigator or according to criteria below:
 - Any suicidal behavior (i.e. actual attempt, interrupted attempt, aborted attempt or preparatory acts or behavior)
 - O Any suicidal ideation of type 4 or 5 in the C-SSRS (i.e. active suicidal thought with intent but without specific plan, or active suicidal thought with plan and intent) that per certified trained mental health professional constitutes a risk of suicidal behaviour
- The Hb drops below 100 g/L (10g/dL) OR Hb decreases by 25% or more from baseline and is below the lower limit of normal.
- The patient can no longer be treated with trial treatment for serious medical reasons (e.g., liver injury, stroke, etc.), per investigator's clinical judgement.
- The patient needs to take any restricted medication that may impact the patient's safety to continue the treatment, per investigator's clinical judgement. Please consult with sponsor.

Page 41 of 112

Proprietary confidential information © 2023 Boehringer Ingelheim International GmbH or one or more of its affiliated companies

- Pregnancy: if a patient becomes pregnant during the trial the study medication will be stopped, the patient will be discontinued from the trial and the patient will be followed up until the birth of the child or otherwise termination of the pregnancy.
 - For further information, including the process for follow-up on the outcome of the pregnancy please see Section 5.2.6.2.3.

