7. STATISTICAL METHODS AND DETERMINATION OF SAMPLE SIZE

The primary efficacy objective is to assess the absolute difference in adjusted mean change from baseline to Week 26 in MCCB overall composite T-score (cognition) for once daily oral treatment with Iclepertin 10mg QD as compared with placebo in patients with CIAS. The key secondary efficacy objectives are to assess the absolute difference in adjusted mean change from baseline to Week 26 in SCoRS interviewer total score and adjusted total time T-score in VRFCAT between Iclepertin 10mg QD and placebo. Intercurrent events will be addressed using a strategy that differs depending upon the nature of the intercurrent event.

The treatment effect for the following treatment policy is of interest: patients remain on randomized treatment for the duration of the trial unless an exacerbation or acute episode or an event considered to be drug-related interrupts or discontinues treatment. Changes in background medication or non-pharmacological intervention are allowed.

Estimation will assume that the policy is followed by all randomized patients. All measurements obtained for patients while on this policy are therefore relevant for the estimation of the primary estimand, while measurements obtained after a deviation from this policy are not relevant for the estimation of the primary estimand.

The following intercurrent events are considered to form part of the treatment policy being assessed and hence subsequent measurements are included in the primary analysis of the endpoint:

- Change in background medication (e.g. antipsychotics, etc.)
- Change in non-pharmacological therapy (e.g. cognitive therapy, any kind of psychotherapy, nicotine withdrawal therapy, diet, etc.)
- Exacerbation or acute episode which results in interruption or early termination of treatment
- Investigator assessed drug-related AEs which lead to early termination of study medication
- Protocol-defined drug withdrawal due to treatment, e.g. haemoglobin decrease, concomitant medications with CYP3A4 substrates
- Change in study partner in the assessment of functional capacity, e.g. SCoRS.

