All other intercurrent events are considered to represent breaks from the treatment policy and therefore confound estimation of the treatment effect of interest. Such intercurrent events would include, for example, early termination of treatment due to reasons unrelated to treatment (e.g. consent withdrawal, incarceration, somatic illness like stroke, cardiovascular events, etc., hospitalization due to somatic illness). Measurements after these intercurrent events are excluded from the primary analyses.

Page 77 of 112

Proprietary confidential information © 2023 Boehringer Ingelheim International GmbH or one or more of its affiliated companies

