Temporary treatment discontinuation or interruption due to other reasons	Identified from data collected in the Temporary Discontinuation page of the CRF.	Hypothetical – only data collected from the end of REP after the interruption, to end of the interruption will be subject to exclusion from the analysis
Temporary treatment-switch	Identified from the dispensation records. Temporary treatment-switch will be handled as temporary interruptions in the same way for	Hypothetical – only data collected from the end of REP after the treatment switch, to end of the

due to dispensation error	both directions (iclepertin to placebo or placebo to iclepertin)	treatment switch will be subject to exclusion from the analysis			
Early Perman	Early Permanent Treatment Discontinuation				
Exacerbation or acute episode of schizophrenia resulting in early termination of treatment	Identified from data collected in the Adverse Event page of the CRF:  - "Drug Withdrawn" reported in the Action Taken with Study Treatment field, and  - Category reported as "Schizophrenia Relapse" or MedDRA preferred term coded as	Treatment policy			
Investigator assessed drug- related adverse events which lead to early termination	"Schizophrenia"  Identified from data collected in the Adverse Event page of the CRF:  - "Drug Withdrawn" reported in the Action Taken with Study Treatment field, and	Treatment policy			
of study medication	- "Yes" reported in the Relationship to Study Treatment field				
Protocol-defined drug withdrawal due to treatment – haemoglobin decrease	Identified from data collected in the End of Treatment and Adverse Event pages of the CRF and laboratory data:  - Subject who did not complete the planned treatment period as reported in the End of Treatment page with reason being "Adverse Event", and  - AE indicating haemoglobin decrease with action taken being "Drug Withdrawn"	Treatment policy			
Protocol-defined drug withdrawal due to treatment – CYP3A4 inhibitors or CYP3A4 sensitive drugs with NTI	Identified from data collected in the End of Treatment page of the CRF:  - Subject who did not complete the planned treatment period as reported in the End of Treatment page with "Protocol Deviation" as the reason, and  - Use of CYP3A4 inhibitors or CYP3A4 sensitive drugs with	Treatment policy			

	NTI specified as the detailed reason of discontinuation	
Early termination of study	Identified from data collected in the End of Treatment page of the CRF:	Hypothetical

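### SAP Table 6.3: 1 keeps medication-driven withdrawals under treatment policy only for CYP3A4 inhibitors or NTI drugs coded as a protocol deviation, which is narrower than the protocol's open category

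*SAP*

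**What the plan says.** **Protocol, estimand.** Section 7 lists the events whose later data stay in the primary analysis. One entry is "Protocol-defined drug withdrawal due to treatment, e.g. haemoglobin decrease, concomitant medications with CYP3A4 substrates". The list is open, but the category is limited to withdrawals due to treatment. Section 2.1.1, like the synopsis, has no such limit: it allows discontinuation for "adverse events (AEs) that are considered drug related and protocol-defined drug withdrawal". Section 7 adds that "All other intercurrent events are considered to represent breaks from the treatment policy", with data after them excluded. Its example is "early termination of treatment due to reasons unrelated to treatment (e.g. consent withdrawal, incarceration, somatic illness like stroke" and similar events.

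**Protocol, withdrawal rules.** Section 3.3.4.2 lists the mandatory stops. They include "The patient exhibits suicidality, in the clinical judgement of the investigator or according to criteria below", a haemoglobin criterion, and "The patient needs to take any restricted medication" with a possible safety impact in the investigator's judgement. Section 4.2.2.1 carries the exclusionary medications of Section 3.3.3 into the treatment period. Exclusion 11 names CYP3A4 inhibitors and, next to them, "Strong or moderate CYP3A4 inducers".

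**SAP.** Table 6.3: 1 has two rows for protocol-defined withdrawal: haemoglobin decrease and medication. The medication row needs two things on the End of Treatment page: Protocol Deviation as the reason, and "Use of CYP3A4 inhibitors or CYP3A4 sensitive drugs with" NTI as the detail. Terminations matching no earlier row go to other AEs or other reasons, both hypothetical. Section 6.3 starts the excluded period at the last dose plus the residual effect period (12 days, Section 6.1).

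**The concern.** The protocol gives examples and the SAP turns them into a closed list with a coding condition. Two kinds of patient are then handled differently from what the protocol category suggests:

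- a patient who must stop under Section 3.3.4.2 because a restricted drug other than an inhibitor or NTI drug is needed, for example a CYP3A4 inducer;
- a patient who stops for an inhibitor or NTI drug, as the SAP row intends, but whose site did not tick Protocol Deviation. A stop under Section 3.3.4.2 follows the protocol, so another code is a reasonable choice.

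In both cases the observed off-treatment MCCB scores are set aside, and the model treats the patient as if still on drug, under missing at random. SAP Sections 7.5.1.1 and 7.5.2 apply the same strategy to the key secondary and other secondary endpoints. At stake is whether the primary analysis estimates the effect that the protocol defines, and whether the data kept depend on a tick-box choice.

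**Working it through.** **1. Restricted-medication stops, side by side**

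| Permanent stop under Protocol 3.3.4.2 | Row in SAP Table 6.3: 1 | Handling |
|---|---|---|
| Inhibitor or NTI drug, coded Protocol Deviation | Medication row | Treatment policy |
| Inhibitor or NTI drug, any other code | Other reasons (other AEs if coded Adverse Event) | Hypothetical |
| CYP3A4 inducer or other restricted drug, any code | Other reasons (other AEs if coded Adverse Event) | Hypothetical |
| Any of these, with a relapse or drug-related AE that led to withdrawal | Relapse or drug-related AE row | Treatment policy, by the precedence rule in SAP 6.3 |

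Rows two and three are the gap. The words due to treatment do not explain it. Needing an inhibitor is no more caused by the trial drug than needing an inducer, yet the SAP labels the inhibitor stop as due to treatment. The NTI limit itself is consistent with the protocol, because Section 4.2.2.1 permits CYP3A4-sensitive drugs without NTI.

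**2. Which scores are lost**

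The early end-of-treatment visit is due within 7 days of the last dose (Protocol 6.2.3.4). Exclusion starts at last dose + 12 days. Since 7 < 12, a timely early visit is not excluded by this rule; from Day 127 it falls in the Week 26 window (SAP Table 6.7: 1), and the separate 28-day MCCB rule of SAP 5.1 still applies. What is lost is any assessment after that 12-day period.

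**3. The plan's own figures (Protocol 7.5)**

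- Inputs: 220 evaluable per arm, standardized effect 0.35, one-sided 0.025.
- Noncentrality = 0.35 × √(220/2) = 3.67. The two-sample t-test then gives 95.57% power. The plan states 95%, and 95.6% in Table 7.5: 1, so it reproduces.
- Randomised total: 440/0.75 = 586.7, against 586 stated. Per arm, 293 × 0.75 = 219.75.

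**4. Illustrative size**

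The documents give no rate for these stops. Let *x* be the assumed share of randomised patients affected. Let *r* be the share with later scores, 25% to 50% (the plan's figure for outcomes collected after early termination). The values lost are taken on top of the planned 25% loss.

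- Extra patients per arm losing later scores = 293 × *x* × *r*
- Effective n per arm = 293 × (0.75 − *x* × *r*), rounded down for power

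| *x* (assumed) | Extra patients per arm | Effective n per arm | Power |
|---|---|---|---|
| 1% | 0.7 to 1.5 | 219.0 to 218.3 | 95.49% to 95.41% |
| 2% | 1.5 to 2.9 | 218.3 to 216.8 | 95.41% to 95.25% |
| 5% | 3.7 to 7.3 | 216.1 to 212.4 | 95.25% to 94.90% |
| 10% | 7.3 to 14.7 | 212.4 to 205.1 | 94.90% to 94.24% |

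The largest power loss is 95.57 − 94.24 = 1.33 points. The 10% row is generous: it would be a quarter to a third of the 30% to 40% projected to terminate early for all reasons.

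For the estimate, take the 2-point MCCB difference from phase II. If the off-treatment benefit were zero and every affected patient were observed, keeping the scores would lower it by 2 × *x*, that is 0.02 to 0.2 T-score points for *x* from 1% to 10%.

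**The case against.** The strongest case for the SAP is that Section 7 governs. Section 2.1.1 refers to Section 7 for the detail, and its own list is a summary. Section 7 limits the category to withdrawals due to treatment and excludes unrelated terminations. The drug-interaction entries in Protocol Table 1.4.2: 1 name the same two classes as the SAP row. The SAP describes itself as a more technical elaboration, so turning examples into rows need not count as a change. The CRF instructions are not available, and needing a prohibited drug could reasonably carry the code Protocol Deviation. Finally, Section 3.3.4.2 applies only where the investigator sees a safety impact.

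Much of this stands, and it rules out stronger readings that a reader might infer:

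- *Every other mandatory withdrawal is wrongly made hypothetical.* Not supported. Relapses and drug-related AEs are treatment policy and take precedence. Consent withdrawal and unrelated somatic illness are excluded by the protocol itself.
- *Suicidality stops not judged drug-related are a clear SAP error.* Not supported. Sections 2.1.1 and 7 differ on the qualifier, so the matter is unsettled.
- *Stops for clozapine, stimulants, tricyclics or ECT are all affected.* Not shown. Nothing visible makes these an automatic withdrawal, and ECT is not a medication.
- *The excluded scores come mostly from deteriorating patients.* The documents say nothing on this, and stops for relapse are already kept.

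The objection does not explain why inhibitors and inducers, restricted side by side in exclusion 11, get opposite handling. Nor does it explain why an inhibitor stop should depend on one reason code.

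**Conclusion.** The point holds for restricted-medication stops. SAP Table 6.3: 1 closes a category that the protocol leaves open and adds a reason-code condition that the protocol does not have; the visible SAP Section 4 does not record either. For suicidality stops not judged drug-related, the documents support only the conclusion that the protocol must be reconciled and the choice stated.

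The effect is probably small. Under the assumed 1% to 10%, it is about 1 to 15 patients per arm and at most about 1.3 power points. A reader might infer a threat to sample size, but the figures do not support that. The issue is that the primary estimand should be the same in both documents and should not turn on coding. The supplementary analysis in Protocol 7.2.2 that handles all events by treatment policy would show the impact, but it does not correct the primary definition. The conclusion rests on the visible text; the CRF completion rules and the true rate are unknown.

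**What to change.** Before unblinding:

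1. Widen the medication row of SAP Table 6.3: 1 to any permanent stop under Protocol 3.3.4.2 for need of a restricted medication, CYP3A4 inducers included. Identify it from the concomitant-medication records and the End of Treatment detail, whatever reason code was ticked.
2. For suicidality stops not judged drug-related, reconcile the synopsis and Section 2.1.1 (no qualifier) with Section 7 (due to treatment; unrelated terminations excluded), and state the chosen strategy in the table.
3. If a narrower category is intended, record it with a reason in SAP Section 4.

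This concerns only how the data are classified for analysis, not who must stop treatment. The cost is SAP wording, a clarification of the protocol's estimand text and the derivation code for intercurrent events. No new data are needed and the sample size does not change.

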#### 6.4 SUBJECT SETS ANALYSED

The following patient analysis sets are defined:

- Screened Set (SS): includes all patients who signed informed consent and were screened for the trial with at least one screening procedure done at Visits 1 or 1a.
- Randomised Set (RS): includes all patients who signed informed consent and were randomised into the trial, regardless of whether a patient was treated with trial medication. Patients randomized in error and discontinued from the study before the start of trial medication will be excluded from the RS. Patients in RS will be analysed under the randomized trial medication. The RS will be used for efficacy analyses as well as demographics and baseline characteristics.
- Treated Set (TS): includes all patients who signed informed consent and were treated with at least one dose of the trial medication. Patients in TS will be analysed under the actual trial medication received at randomisation. The TS will be used for safety analyses.

#### 6.6 HANDLING OF MISSING DATA AND OUTLIERS

Missing or incomplete AE dates will be imputed according to BI standards (1). Missing data and outliers of PK data will be handled according to (2).

If not specified otherwise, missing data will not be imputed and will remain missing. Potential outliers will be reported and analysed as observed.

Handling and derivation of total/domain/subscale scores for the assessment scales in case of missing individual item scores are specified below:

#### **MCCB**

Handling of missing data in MCCB tests will follow the MCCB Manual (available in the ISF). See Section 10.1 for detailed descriptions and imputation rules.

#### **SCoRS**

For the 20-item SCoRS assessment, if six or more of the 20 items have missing response, which includes the response of "N/A", for a subject at a visit, then the SCoRS total score for that subject at that visit is missing. If five or less of the 20 items have missing response, which includes the response of "N/A", for a subject at a visit, then the item with missing response will be imputed first with the average of the non-missing item values for the subject at the visit, and then SCoRS total score for the subject at the visit will be derived as the sum of the non-missing item values and the imputed item values.

